4.1 Study Design

The trial will follow a Bayesian Optimal Interval (BOIN) design to guide escalation and de-escalation decision, establish a maximum tolerated dose (MTD), and identify a dose and schedule of RP-1664 that is tolerable.

All participants will undergo a PK evaluation period starting at Cycle 0 Day 1. Participants will be assigned to receive either a single dose of RP-1664 at the highest Safety Review Committee (SRC) approved dose level with PK collection over the subsequent 48 hours to characterize the half life (t1/2) of RP-1664 in the fasted state or enrolled into a cohort to investigate the effect of food on RP-1664 PK.

The starting dose (Dose Level 1) is 10 mg once daily (QD). RP-1664 will initially be given QD on a 2 weeks on 1 week off schedule to allow 1 week for bone marrow recovery.

The first escalation (Dose Level 2) will be up to 30 mg to limit the number of participants receiving a potentially subtherapeutic dose. After Dose Level 2, escalation will proceed with up to 100% increases in RP-1664 after evaluation of tolerability by the SRC until Dose Level S. Dose Level S is defined as the dose level at which any of the following safety signals occur during Cycle 0 or Cycle 1:

- Any \geq Grade 3 hematological toxicity
- >50% decrease in platelets or neutrophils from Cycle 0 Day 1
- >2 g/dL decrease in hemoglobin from Cycle 0 Day 1
- Any ≥ Grade 2 drug-related non-hematological toxicity lasting >5 days or requiring clinical intervention, except Grade 2 fatigue, nausea, vomiting, diarrhea, or constipation
- Any adverse event (AE) of any grade limiting tolerability as assessed by the SRC

At Dose Level S, the cohorts will be expanded to a minimum of 3 participants to further evaluate safety, PK, and pharmacological activity. Evidence of pharmacologic activity can include Grade ≥ 2 drug-related toxicity at any cycle, PK

data demonstrating exposure levels predicted to be efficacious based on nonclinical studies, or other evidence of treatment-related activity as agreed on by the SRC. Dose decisions will be based on assessments in 2 or more dose-limiting toxicity (DLT) evaluable participants completing the DLT evaluation period. Any escalation of RP-1664 after Dose Level S will be in increments up to 75% as agreed upon by the SRC and will enroll cohort sizes of $N \ge 3$.

RP-1664 Escalation Dose Level	Escalation Plan
	Daily (mg) or % of previous dose
	increment
1	10 mg
2	Up to 30 mg
3 to S	Up to 100% increases until Dose Level S

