6.1 DLT Evaluable Population

The DLT Evaluable Population will consist of participants who have met the minimum safety evaluation requirements of the trial and /or who experience a DLT at any time during the DLT evaluation period (from the start of treatment through the end of Cycle 1). Minimum safety requirements will be met if, during Cycle 1 of treatment, the participant receives at least 75% of their planned total dose of RP-1664, completes required safety evaluations, and is observed through the end of Cycle 1. This analysis set will be used for DLT analyses, unless otherwise specified.

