12.1 Dose Limiting Toxicities

The number of DLTs will be summarized by treatment arms for the DLT Evaluable Population. A toxicity will be considered a DLT if it occurs from the first dose to the end of Cycle 1 (including the PK evaluation period), meets the pre-defined criteria for DLTs, is deemed at least possibly related to trial treatment, and is not clearly and incontrovertibly due to disease progression or extraneous cause. Toxicity will be assessed using CTCAE v 5.0, unless other specified. Details of DLTs will be listed.

DLTs will be defined as any of the following:

Any death not clearly due to the underlying disease or extraneous causes

Hematologic TEAES:

- Grade 4 neutropenia
- Febrile neutropenia (defined as absolute neutrophil count (ANC) <1000 cells/ μ L with a single temperature of 38.3°C [100.4°F] for > 1 hour).
- Grade 4 thrombocytopenia or Grade 3 thrombocytopenia associated with Grade \geq 2 bleeding.
- Grade 4 anemia or Grade 3 anemia requiring red blood cell (RBC) transfusion given to participants with documented anemia-related symptoms.

Non-Hematologic TEAEs:

- Any Grade \geq 3 TEAE except the below
 - 1. Grade ≥ 3 non-hematologic laboratory abnormalities that are asymptomatic and respond to medical intervention or resolve to grade 1 in \leq 72 hours.
 - 2. Grade 3 fatigue with duration < 7 days
 - 3. Grade \geq 3 nausea/vomiting/diarrhea that lasts \leq 72 hours and resolves with or without optimal supportive care.
 - 4. Grade \geq 3 amylase or lipase elevation not associated with symptoms or clinical manifestations of pancreatitis.
 - 5. The use of red blood cell transfusion for anemia Grade <3 or the use of G-CSF for Grade <4 neutropenia
- Symptomatic Grade ≥ 3 QTc prolongation (QTcF ≥ 501 msec on at least two separate electrocardiogram (ECGs)), or asymptomatic Grade ≥ 3 QTc prolongation that has been confirmed by repeat testing and reevaluation by a qualified person and persists after correction of reversible causes such as electrolyte abnormalities or hypoxia.
- Drug-induced liver injury meeting Hy's Law criteria defined as:
 - 1. ALT or AST ≥3-fold above the Upper Limit of Normal (ULN) or 5.0 x ULN in the case of liver metastases at baseline and
 - 2. Serum total bilirubin \geq 2-folde above ULN (without findings of cholestasis) and
 - 3. Alkaline phosphatase $\leq 2 \times ULN$ and
 - 4. No other overt reason for liver injury

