12-lead ECG ^m		X	X				X				X		X		X			X				
Pregnancy test ⁿ		X	X								X				X			X		X	X	
Clinical safety lab tests ^o		X	X								X				X			X		X	X	
CBC with diff. (included in safety lab tests)													X	X		X	X		X ^h			
ctDNA whole blood ^p		X	X								X		X			X		X ^h	X ^h	X		
Tumor biopsy ^{q,r,s}		X^q														X ^r				X ^s		

				Cycle 0																									
	Dwa						Food I			r	PK Cycle ^b								Additional		EOT/	Safety	Survival						
	Pre- screening	Screening ^a	Ef For	fect mul l (P		on	Effe Form	Fasted (Food Effect) or Formulation 2 (PK Bridging)			Effect) or brmulation 2			Fasted	Fasted			Cycle 1				Cycle 2				tional cles	ET ^c	Follow -up Visit ^d	Follow- up ^e
Trial Days Procedures/ Assessments ^f	-180 to -1	-28 to -1	1 ^a	2	3	4	5 (+5)	6	7	8	1ª	1	8 (+2		15 (+2)	1 (+3)	8 (+2)	15 (+2)	1 (+3) ^g	8 (+2) ^h	Within +7 days of Disc of Trt date	30 days after last dose (+14 days)	Every 90 days (±14 days)						
Central testing for molecular eligibility ^t	X																												
Archival tumor tissue ^u	X ^t	X																											
RP-1664 dispensed/coll ected				Dispensed and collected according to Pharmacy Manual																									
RP-1664 administration			X See Section Error! Reference source not found., Dosing and Administration																										
Review of dosing diary ^w												X	X		X	X	X	X	X		X								
PK sample collection ^x			X	X	X	X	X ^y	Х	X	X	X ^z	X	Xz	:		X ^z	Xz		Xz										

			PK	Cvcl	e Foi	Cycl		ct o	r	PK											
	Pre-			PK I	Bridg	ging Col				Cycle ^b	_						Addi	tional	EOT/	Safety Follow	Survival
	screening	Screening ^a	Ef For	d (Fo fect) mula 1 (PK idgin	or tion	Faste Eff Form (PK l	ect) ulat	or tion	2	Fasted		Cycl	e I		Cycle 2		Cy	cles	ET°	-up Visit ^d	Follow- up ^e
Trial Days	-180 to -1	-28 to -1	1 ^a	2	3 4	5 (+5)	6	7	8	1 ^a	1	8 (+2)	15 (+2)	1 (+3)	8 (+2)	15 (+2)	1 (+3) ^g	8 (+2) ^h	Within +7 days of Disc of Trt	30 days after last dose	Every 90 days (±14 days)
Procedures/ Assessments ^f																			date	(+14 days)	
Blood collection (4β- OHC/total cholesterol) ^{aa}		X	X										X		X			X			
Urine collection ^{bb}						X															
Tumor assessments: RECIST or INRC ^{cc}		X^{dd}									Т			tumor a		nts. Ther	om Cycle eafter, e				
Serum tumor markers ^{ee}		X	7	To be	asses	sed at l	east	onc	е ре	er cycle fro	cycle from Cycle 0 Day 1 and at EOT (or as per standard of care schedule).										

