- f. **Procedures/Assessments:** Pre-screening for molecular eligibility can take place up to 180 days before first dose of RP-1664. Screening procedures and tumor assessment must be performed within 28 days before first dose of RP-1664.
- g. **CXD1:** The start of a new additional cycle should always coincide with the start of RP-1664 administration for that cycle. A +3-day window is allowed for the start of new cycles, though cycles should never start early and should be at least 21 days in length. A -2-day window is allowed for the assessments scheduled for the CXD1 visit to enable flexibility with visit scheduling.
- h. **Day 8 of Additional Cycles:** CBC and vital signs to be assessed only on C2 and C3. Labs and vital signs can be done locally at these timepoints as long as they are reviewed by the research team on the day of draw. For Cycle 3, ctDNA should be collected on Day 8 and not on Day 1, however for Cycles 4 and up, ctDNA should be collected on Day 1. Blood samples for 4β-OHC and total cholesterol are only collected up to Cycle 3.
- j. Abbreviated PE: Starting at Cycle 2, abbreviated PE to be performed every 2 cycles (unless full PE necessary by Investigator judgment).
- k. **Height:** Pediatric participants will have their height measured every 3 cycles.
- l. Vital Signs: Blood pressure, heart rate, and temperature to be measured after the participant has been sitting for 5 minutes.
- m. ECG: 12-lead ECGs to be done in triplicate ≥ 1 minute apart per Table 2. The triplicate ECG measurements must occur within a 30 minute time period. Participants should be in supine position and resting for at least 10 minutes before trial-related ECGs. QTcF should be recorded (QTcB is not required). Participants in the food effect or PK bridging portion of the trial should have ECGs collected per Table 11 and Table 12, respectively.
- n. **Pregnancy Test:** For women of childbearing potential, a serum pregnancy test is required at Screening. If pregnancy test was done within 96 hours of Cycle 0 Day 1, repeat testing is not required. A serum or urine pregnancy test must be performed on Day 1 of each cycle starting on Cycle 2, at EOT, and at the Safety Follow-up visit. A pregnancy test can be performed more frequently if required per local regulations.

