- o. Clinical Safety Laboratory Tests: Clinical laboratory tests (including serum or plasma chemistry, hematology [including reticulocyte count], and urinalysis) will be performed at local laboratories according to the laboratory's normal procedures. See Section Error! Reference source not found. for a complete listing of laboratory tests to be performed.

- q. **Baseline Tumor Biopsy:** If archival tissue does not meet trial requirements, a pre-treatment biopsy during Screening is mandatory. If a biopsy cannot be safely performed, the participant may still be eligible with prior Sponsor approval. If the participant is providing paired biopsies, a pre-treatment and an on-treatment biopsy are mandatory. Biopsy tissue must be shipped to the Sponsor-designated lab during Screening or by Cycle 1 Day 1 (+7 days). Bone tissue is not acceptable for tumor tissue submission because bone biopsies require a decalcification step that will interfere with downstream processing of the sample. *US only:* Participants 12 to 17 years of age are not required to provide a biopsy.
- r. **On-treatment Tumor Biopsy**: This assessment applies only to participants providing a paired tumor biopsy. Biopsy should be collected on Cycle 2 Day 8 (+2), 2 to 6 hours after dosing of RP-1664. Participants must have taken a minimum of 7 consecutive days of RP-1664 prior to on-treatment biopsy collection. If biopsy collection at this timepoint is not possible, please contact the Sponsor to schedule an appropriate time for on-treatment biopsy.
- s. **Post-Progression Tumor Biopsy:** An optional tumor biopsy will be requested post-progression for participants with prior confirmed responses or stable disease ≥ 16 weeks.
- t.
- Mandatory Archival Tumor Tissue: Archival tissue is to be submitted to the Sponsor-designated lab during Screening. Refer to Laboratory Manual for further details. If adequate archived tumor tissue is not available and/or a fresh biopsy cannot be safely performed, the participant may still be eligible with prior Sponsor approval. The Sponsor prefers archival material from the primary tumor if available.
- v. **RP-1664 Administration:** Cycle 0 dosing should start Monday to Wednesday, if unable to accommodate weekend visits. A +5-day window is allowed prior to initiating the Cycle 0 Day 5 Fasted PK or PK bridging blood collection.

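### The released schedules mark no chemistry panel between the baseline draw and Cycle 2 Day 1, yet chemistry-based DLTs are counted to the end of Cycle 1

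*SAP*

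**What the plan says.** **The panel.** In SAP 14.1.1 the safety-laboratory row is defined in its footnote (o in Tables 1, 5, 7 and 9; p in Table 3) as "Clinical laboratory tests (including serum or plasma chemistry, hematology [including reticulocyte count], and urinalysis". In each table it is marked at Screening, Cycle 0 Day 1, Cycle 2 Day 1, Day 1 of later cycles, end of treatment and Safety Follow-up. The footnote refers to another section for the list of tests; that section is not in the released text.

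**Cycle 1.** A separate row, "CBC with diff. (included in safety lab tests", is marked on Days 8 and 15 in Tables 1, 3 and 5, on Days 7, 15 and 22 in Table 7, and on Days 8, 15 and 22 in Table 9.

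**DLT window.** SAP 12.1 counts a toxicity "if it occurs from the first dose to the end of Cycle 1 (including the PK evaluation period". The criteria include Hy's Law and any non-hematologic event of Grade 3 or higher. Exception 1 removes "non-hematologic laboratory abnormalities that are asymptomatic and respond to medical intervention or resolve to grade 1 in" 72 hours or less. A further exception removes amylase or lipase elevations without signs of pancreatitis.

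**Evaluability.** Besides a minimum dose, SAP 6.1 asks that a DLT-free participant "completes required safety evaluations, and is observed through the end of Cycle 1". It does not list the evaluations.

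**Dose Level S.** SAP 4.1 and the protocol synopsis define it by "safety signals occur during Cycle 0 or Cycle 1". One of these is Grade 2 or higher "drug-related non-hematological toxicity lasting >5 days or requiring clinical intervention", with no exception for laboratory findings. After Dose Level S the step limit changes from up to 100% to up to 75%, with cohorts of at least 3.

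**The concern.** Hy's Law needs transaminases, bilirubin and alkaline phosphatase. An asymptomatic Grade 3 chemistry abnormality can be seen only if blood is drawn for chemistry. Between the baseline draw and Cycle 2 Day 1 the released schedules ask for none. A participant can therefore complete everything marked for Cycle 1, count as evaluable and enter the tally as DLT-free, although part of the DLT definition was never measured.

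The error runs one way: an unmeasured event is recorded as no event, which favors escalation. SAP 4.1 lets dose decisions rest on 2 or more evaluable participants, so single participants carry weight. The Dose Level S rule uses the same window, and a Grade 2 chemistry abnormality lasting more than 5 days cannot be established there from scheduled labs.

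**Working it through.** The plan states no figure to reproduce, so the check is a count of marks and an interval calculation.

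**1. Marks on Cycle 1 visits** (rows aligned to the Trial Days header of each table)

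| Table | Schedule | Cycle 1 visits | Chemistry-bearing panel | CBC |
|---|---|---|---|---|
| 1 | 2 weeks on/1 off | 3 | 0 | 2 |
| 3 | 3 days on/4 off | 3 | 0 | 2 |
| 5 | daily | 3 | 0 | 2 |
| 7 | 1 week on/1 off | 4 | 0 | 3 |
| 9 | 2 weeks on/2 off | 4 | 0 | 3 |
| Total | | 17 | 0 | 12 |

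Later Cycle 0 days carry no panel mark either, including Day 5, when food-effect and bridging participants take their second dose. The 4β-OHC/cholesterol sample is a separate collection, not a safety chemistry panel.

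**2. First dose to first post-dose panel** = Cycle 0 length + Cycle 1 length. Assumed Cycle 0 length: 2-3 days (standard; the PK footnote says 2 days, sampling runs 48 hours), or 8 days up to 8 + 5 = 13 days (food effect or bridging, with the +5-day window before Day 5).

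- Standard: 2 + 21 = 23 to 3 + 21 = 24 days; 2 + 28 = 30 to 3 + 28 = 31 days.
- Food effect or bridging: 8 + 21 = 29 to 13 + 21 = 34 days; 8 + 28 = 36 to 13 + 28 = 41 days.

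**3. Last Cycle 1 dose to Cycle 2 Day 1** = cycle length + 1 − last dosing day.

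- 2 weeks on/1 off: 22 − 14 = 8 days.
- 1 week on/1 off: 29 − 21 = 8 days.
- 2 weeks on/2 off: 29 − 14 = 15 days.
- 3 days on/4 off: 22 − 17 = 5 days.
- Daily: 22 − 21 = 1 day.

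**4. What can go unseen.** The event must meet all of these conditions:

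- It is Hy's Law, or a Grade 3 or higher chemistry abnormality other than an excepted amylase or lipase elevation.
- It is asymptomatic.
- It falls outside exception 1.
- It has recovered before Cycle 2 Day 1.
- No unscheduled draw caught it.

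Not affected: hematologic DLTs, symptomatic toxicity, ECG-detected QTc events, abnormalities still present at Cycle 2 Day 1, and participants who stop in Cycle 1 and have the end-of-treatment panel.

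**5. Effect of adding chemistry to the Cycle 1 CBC draws** (nominal days). First dose to first panel becomes 2 + 6 = 8 (Table 7) to 3 + 7 = 10 days with the standard Cycle 0, or 8 + 6 = 14 to 13 + 7 = 20 days for food-effect or bridging participants. Later nominal intervals are 7-8 days. Within the +2-day windows, Day 8 can be Day 10, and 15 − 10 = 5 days; in Table 7, Day 15 can be Day 17, and 22 − 17 = 5 days.

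**The case against.** **The laboratory section is not released.** Only the synopsis of the protocol is available, and the footnote's cross-reference is broken, so Cycle 1 chemistry may be required elsewhere. This stands as a limit on confidence. It does not remove the conflict, because the rows that set visit timing are released and the footnote points elsewhere only for the list of tests.

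**Cycle 2 Day 1 may fall inside the window.** A footnote says: "A -2-day window is allowed for the assessments scheduled for the CXD1 visit". If it covers Cycle 2 Day 1, the panel could be drawn on the last two days of Cycle 1, with 6, 6, 13 and 3 days off drug on the four intermittent schedules in the order of step 3. But its marker sits on the Additional Cycles column, and using the window is optional.

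**Unscheduled labs are graded** (SAP 7.3 and 12.3). True if they are drawn; nothing released requires them.

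**Weekly CBC with chemistry once per cycle fits a drug whose anticipated toxicity is neutropenia.** That explains the choice. It does not supply the data for the chemistry criteria in SAP 12.1.

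**Dose Level S has other routes:** clinical intervention, intolerability judged by the Safety Review Committee (SRC), and hematologic signals. Agreed. Only the duration route for chemistry is affected.

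**A stronger inference to resist.** A reader might infer that one missed event would reverse a dose decision. Under assumed BOIN targets of 0.20-0.33 with default boundaries (escalate below 0.157-0.260, de-escalate above 0.238-0.395), 0 of 2 is escalate and 1 of 2 is de-escalate throughout. But no target is visible in the documents, BOIN only guides the SRC, and nothing shows how often such an event would occur.

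**Conclusion.** The inconsistency holds in the released text: 0 of 17 Cycle 1 visit columns carry chemistry, while SAP 12.1 counts chemistry-based DLTs over that window and SAP 6.1 does not ask for the data. It should be fixed. Confidence is medium because of the unreleased laboratory section.

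Its size is a gap in scheduled observation: 23-24 or 30-31 days, and 29-34 or 36-41 days for food-effect and bridging participants. It ends 5-15 days off drug on the intermittent schedules and matters least on daily dosing. The resulting bias is confined to transient, asymptomatic chemistry events and runs toward escalation. Its frequency and its effect on BOIN decisions cannot be derived. The intervals assume nominal visit days and the Cycle 0 lengths given in the working.

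A reader might also infer that the trial cannot detect liver or chemistry toxicity. The documents do not support that: a full panel is marked at Day 1 of every cycle from Cycle 2 and at end of treatment, and unscheduled results count.

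**What to change.** Reconcile the Schedule of Activities with SAP 12.1 and 6.1.

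1. If the laboratory section already requires Cycle 1 chemistry, mark it in the five tables. If not, run the chemistry part of the existing safety panel on the Cycle 1 CBC draws already scheduled: two in Tables 1, 3 and 5; three in Tables 7 and 9.
2. For participants enrolled after the change only, name post-dose chemistry among the required evaluations in SAP 6.1. For earlier cohorts, list the DLT-evaluable participants who had no post-dose chemistry in the window; do not remove them.
3. State whether the -2-day window applies to Cycle 2 Day 1.

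The added panels should not be presented as establishing a duration of more than 5 days or resolution within 72 hours. They can be 5 days apart, so judging either would still need a repeat draw after an abnormal value. On 3 days on/4 off, nominal Days 8 and 15 each come 5 days after the previous dose, so the gain there is a shorter interval and not an on-drug value.

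Cost: two or three extra local chemistry panels per participant with no new visit, one schedule amendment across sites, one sentence in SAP 6.1, and possibly a few replacements for later participants who miss the draw. If chemistry is already required, the cost is wording only.
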